#### **Analysis of Primary Endpoint:**

We will first compare the proportion of patients with at least 1 readmission, ER visit or unplanned urgent clinic visit for HF or death between the two study groups, using Chi-squares test or Fisher’s Exact tests. Logistic regression will be conducted to adjust for the effects of other potential confounders (e.g. age, gender). Stepwise, backward, or forward model selection strategy will be adopted to determine the variables to be included in the final model. Standard diagnostic and model checking procedures,

such as deviance residual plot and Hosmer- Lemeshow test, will be applied to examine the fit of the developed models.

**Analysis of Secondary Endpoints:** The secondary endpoints include continuous longitudinal outcomes (e.g. change in KCCQ score from baseline at 6, 12, and 26 weeks), and discrete outcomes (e.g. whether patients with a  $\geq 5$ pts increase in KCCQ score). To analyze continuous longitudinal outcomes, we will first conduct cross-sectional analyses based on nonparametric Wilcoxon tests (or t-tests), followed by multivariate linear regression, where responses may be transformed to better meet the normality assumption. Then we will apply repeated measures ANOVA or repeated measures linear regression model to assess the outcome differences between the two study groups, simultaneously evaluating the outcomes measured at different time points while appropriately accommodating the within-subject correlations. For discrete outcomes, we will conduct univariate analyses based on Chi-square tests (or Fisher's Exact tests). For binary discrete outcomes, we will use logistic regression models to account for the effects of other potential confounders. For other types of discrete outcome (e.g. counts), we will apply Poisson regression models or Negative Binomial regression models to address the confounding effects of other variables. Standard model selection and checking procedures will be applied to ensure the adequacy of the adopted models.

**Cost-Effectiveness Analyses:** The endpoints include healthcare charges, and numbers and incidences of emergency room visits, urgent clinic visits for HF, and hospitalizations. For continuous outcomes (e.g. charges), we will use Wilcoxon rank-sum test to compare them between the two groups. Linear regression or quantile regression will be performed to assess the group difference adjusting for other potential confounders such as baseline utility scores. The Chi-square test will be used to compare categorical outcomes (e.g. categorized frequency of emergence room visits), followed by generalized linear models (e.g. logistic regression model) which adjusts for other potential confounders. To model repeatedly measured cost-related outcomes (e.g. utility scores) over time, repeated measures analyses via linear mixed models or generalized linear mixed model will also be performed to estimate the effect of dapagliflozin, time, and their interaction. Potential covariates such as age, gender, race, insurance, and duration of T2D, along with baseline utility score, will be adjusted. Standard model selection and checking procedures will be applied to ensure the adequacy of the adopted models.

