### Treatment recommendations at discharge in patients with diabetes

**Study Medications:** Study subjects will be randomized 1:1 to receive either dapagliflozin 10 mg or matching placebo at the time of discharge.

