### **Statistical Methods**

This study is randomized placebo-controlled trial. The overall hypothesis is that dapagliflozin will reduce the rates of the combined outcomes of hospital readmissions, ER visits, clinic visits for HF and death (primary endpoint) and improve symptoms, quality of life and results in a reduction in NT proBNP and resource utilization/costs as compared with placebo in patients with ADHF.

**Sample Size and Power Calculations:** The sample size calculation is based on the primary endpoint measured as the proportion of patients who have hospital readmission, emergency department (ER) visits, and urgent unplanned clinic visit for HF and death during the 26-weeks follow-up period.

Approximately 5.7 million people have been diagnosed with HF in the US . Patients hospitalized for HF are at high risk for readmission, with a 1 and 3-month readmission rate between 20-30%  and a 6-month readmission rate as high as 50% to 60% . An analysis of Medicare data from the Centers for Medicare and Medicaid Services among 28,919 patients with HF hospitalizations, the 6—9 month following the initial HF admission, 60% of patients had 1 or more readmissions for any cause .

Similarly, the national registry of heart failure in Spain with 45.3% of patients with diabetes, a known diagnosis of diabetes was associated with increased all-cause mortality (HR 1.54; 95%CI 1.20–1.97, p = 0.001) and readmissions (HR 1.46; 95%CI 1.18–1.80, p < 0.001). In that study, 40.9% of patients with

diabetes were readmitted within 6-12 months after discharge. An additional study of 462 hospitalized patients with T2D, 44% of the HF events were readmitted to the hospital within 6-month of the primary admission. Thus, our review of the literature indicates that about ~ 40-60% of patients with diabetes with heart failure will be readmitted within 6-month of follow-up.

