SGLT2-is have been shown to markedly reduced HF hospital admissions in patients with and without diabetes. In the CVD-Real Study, which included 961 HF cases, SGLT2-i reduced the rates of HF hospitalizations hazard ratio, 0.61; 95% confidence interval, 0.51-0.73; P<0.001. The CVD-Real 2 multinational study of 235,064 patients with T2D, initiation of an SGLT-2i was also associated with a lower risk of all-cause death and hospitalization for heart failure, as compared to other glucose lowering drugs. The use of SGLT-2i vs. other glucose lowering drugs was associated with lower risk of death and heart failure. Recent RCT examining cardiovascular outcome using SGLT2-i reported a significant reduction in hospitalization for HF. In the DECLARE trial, dapagliflozin resulted in lower rate of hospitalization for heart failure compared to placebo (HR, 0.73; 95% CI, 0.61 to 0.88). The EMPA-REG OUTCOME study showed a 35% reduction in HF hospitalizations. In addition, in the CANVAS Program the benefits were greater in patients with a previous history of HF compared with those without HF at baseline (HR, 0.87; 95% CI, 0.72–1.06; P interaction = 0.021). In the Canvas Program, the rate of HF was reduced in patients with history of HF from 28.1% to 14.1% between patients treated with canagliflozin and placebo.

Based on data summarized above, we assume the composite event rate in the placebo group is between 40-60%, which would be reduced by 30% in the dapagliflozin group. Based on two-sided Chi-square test, with preserved alpha=0.05, with 176 subjects, we would achieve over 80% power to detect a 30% reduction in proportion of patients with readmission, ER visits, urgent unplanned clinic visit for HF or death if the composite event rate in the placebo group is 50%. Accounting for 10% attrition, we propose to recruit 392 patients (196 per group).

In the table below, we provide estimated power based on the same method, corresponding to different placebo composite event rates that are between 40-60%:

Composite event rate in the placebo group	40%	45%	50%	55%	60%
Estimated Power	62%	72%	82%	88%	93%

The results in the above table suggest promising power for the proposed study.

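### The trial is sized on a 30% relative reduction in a proportion, but the primary analysis names no effect measure or confidence interval, and its only adjusted method directly returns an odds ratio

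*Combined protocol and SAP*

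**What the plan says.** Under Statistical Methods, the sample-size paragraph fixes the scale of the endpoint: "The sample size calculation is based on the primary endpoint measured as the proportion of patients who have hospital readmission" and the other listed events over 26 weeks. The planning effect follows: "we assume the composite event rate in the placebo group is between 40-60%, which would be reduced by 30% in the dapagliflozin group". The power statement is on the same scale: "we would achieve over 80% power to detect a 30% reduction in proportion of patients with readmission" (or another component of the composite), at a placebo rate of 50%. The test is also named: "Based on two-sided Chi-square test, with preserved alpha=0.05, with 176 subjects".

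Analysis of Primary Endpoint has two steps. The first is unadjusted: "We will first compare the proportion of patients with at least 1 readmission, ER visit or unplanned urgent clinic visit for HF or death", by chi-square or Fisher's exact test. The second is adjusted: "Logistic regression will be conducted to adjust for the effects of other potential confounders". Age and gender are offered as examples of covariates. The final set is to be found by stepwise, backward or forward selection, and the plan does not say which.

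For the primary endpoint the plan names no risk ratio, risk difference or odds ratio, no confidence interval, no standardisation step and no fixed covariate list. Randomization and Blinding says that randomisation is blocked by diabetes status; the primary analysis does not say that this factor enters the model.

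**The concern.** The design argues in proportions: 50% falling to 35%, for example. The only adjusted analysis is one whose treatment coefficient is a log odds ratio. When about half of the patients are expected to have an event, odds and risks diverge widely, and the rare-outcome approximation is not available.

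Two things follow. First, the adjusted result will not be on the scale of the planning assumption, or of the unadjusted proportions reported beside it. A reader who sets an odds ratio near 0.5 against the planned 30% reduction will think that the drug did much better than planned when it did exactly as planned.

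Second, the odds ratio is non-collapsible: conditioning on a prognostic covariate moves it away from 1 even when the arms are perfectly balanced. Because the data choose the covariates, the quantity that the adjusted odds ratio estimates is not fixed before the analysis.

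**Working it through.** **Inputs from the plan.** Placebo proportion p = 0.40 to 0.60, base case 0.50; relative reduction 30%, so q = 0.7p in the dapagliflozin arm; two-sided alpha 0.05; chi-square test; 176 subjects; 10% attrition; 196 per group; 1:1 allocation.

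**Step 1: reproduce the plan's figure.** Read 176 as the number per group. With p = 0.50, q = 0.35 and mean 0.425:

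z = [0.15 × √176 − 1.96 × √(2 × 0.425 × 0.575)] / √(0.50 × 0.50 + 0.35 × 0.65) = (1.990 − 1.370) / 0.691 = 0.897

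This gives power of 81.5%, against 82% in the table. With 88 per group the power would be 52%, so 176 must be per group. Attrition: 176 / 0.90 = 195.6, rounded up to 196, as stated. The planning effect is therefore confirmed as a risk ratio of 0.70 on proportions. (The table entries at 40% and 45% do not reproduce with this formula: 66.3% against 62%, and 74.3% against 72%. That is a separate matter and does not bear on this point.)

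**Step 2: put the planning effect on the odds scale.** Odds ratio = [q/(1−q)] / [p/(1−p)].

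| Placebo p | Dapagliflozin q | Risk ratio | Risk difference | Odds ratio | Reduction in odds |
|---|---|---|---|---|---|
| 40% | 28% | 0.70 | 12 points | 0.583 | 42% |
| 50% | 35% | 0.70 | 15 points | 0.538 | 46% |
| 60% | 42% | 0.70 | 18 points | 0.483 | 52% |

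For the base case: (0.35/0.65) / (0.50/0.50) = 0.538.

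In the other direction, an odds ratio of 0.70, which would look like the planned effect, is a risk ratio of only 0.80, 0.82 or 0.85 at 40%, 50% or 60%. At 50%: treated odds 0.70, treated risk 0.70/1.70 = 0.412, risk ratio 0.412/0.50 = 0.82.

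**Step 3: dependence on the covariates.** The documents give no prognostic strength, so this step rests on an assumption, shown as a range. Let the covariates kept in the model form a score that is normal with standard deviation s on the log-odds scale and has the same distribution in both arms (no confounding). Hold the marginal risks at 50% and 35%. For each s, find the intercepts a and b for which the average of 1/(1 + exp(−(a + sZ))) is 0.50 and the average of 1/(1 + exp(−(b + sZ))) is 0.35, with Z standard normal. The conditional odds ratio is exp(b − a).

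| Assumed s | Conditional odds ratio | Risk ratio |
|---|---|---|
| 0 (no covariates) | 0.54 | 0.70 |
| 0.5 | 0.52 | 0.70 |
| 1.0 | 0.47 | 0.70 |
| 1.5 | 0.42 | 0.70 |

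For scale, s of 0.5, 1.0 and 1.5 corresponds to a c-statistic of about 0.63, 0.74 and 0.81 for the covariate score. The drug effect on the proportions is identical in every row. Only the covariate set changes.

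**The case against.** The strongest reply is that nothing essential is broken. The first-listed analysis compares proportions with the very test that was powered. In a 1:1 randomised trial that contrast is unbiased, and a reader who has the two proportions can work out the risk ratio and the risk difference. All of this stands. What remains is that the plan names tests and no estimate or interval, and that the adjusted result would still appear on another scale.

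Four stronger readings are tempting, and the documents do not support them.

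- A reader might infer that the trial's hypothesis is a 30% reduction. It is not. The hypothesis under Aim 1, and the overall hypothesis under Statistical Methods, say only that the rate will fall. The 30% is a planning assumption in the power calculation.
- A reader might infer that the plan commits itself to an odds ratio. It never uses the term. The odds ratio is what a logistic model directly gives when no further step is named, and a logistic model can equally be used to produce standardised risks.
- A reader might infer that an odds ratio is biased or exaggerates the effect. It is a valid measure that answers a different question. It misleads only when it is read as a reduction in risk.
- A reader might infer that the power or the primary test is invalid. Neither is touched.

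It is also fair to say that covariate dependence is the smaller part. If the selected covariates are weak (s = 0.5), the odds ratio moves only from 0.54 to 0.52. Most of the distance from 0.70 to about 0.5 is the change of scale.

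Finally, standardising after an open selection procedure would not be enough. The target would be fixed, but the estimate and its interval would still depend on a procedure that is not specified. The covariates have to be settled as well.

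**Conclusion.** The point holds as a gap in what the primary analysis will report. The planning effect is a risk ratio of 0.70. The plan specifies no effect measure or interval, and the one adjusted method that it names directly returns an odds ratio of 0.58, 0.54 or 0.48 for that same effect at placebo rates of 40%, 50% or 60%. These figures follow from the plan's own inputs by arithmetic alone.

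The further movement with covariates, from 0.54 to between 0.52 and 0.42 at 50% versus 35%, rests on an assumed normal covariate score with a log-odds standard deviation of 0.5 to 1.5. The direction of the shift does not depend on that choice, but its size does.

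This should be changed before the data are analysed, because it affects how the adjusted primary result is read. It does not affect the type I error, power or validity of the unadjusted chi-square test.

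**What to change.** Amend Analysis of Primary Endpoint as follows.

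1. Beside the chi-square test, report the unadjusted risk difference and risk ratio, each with a 95% confidence interval.
2. Replace the selection procedure with a list of baseline covariates fixed in advance. Include diabetes status, since randomisation is blocked on it.
3. Keep the logistic model, and take the adjusted estimate from it by standardisation: predict each patient's risk under each arm, average over all patients, and report the two marginal risks with their risk difference and risk ratio and delta-method or bootstrap 95% confidence intervals.
4. Give the adjusted odds ratio as a supplement, labelled as conditional on the listed covariates.

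The cost is a few lines of SAP text and a little more analysis code. No new data or patients are needed, and the planned test and its power are unchanged. The one price is presentational: the headline adjusted effect will look smaller than an odds ratio would, for example 0.70 in place of 0.54 in the base case.

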#### **Randomization and Blinding**

This is a double blinded, randomized, placebo-controlled trial in patients with heart failure. Computer-generated randomization tables will be provided by [name] at the Emory School of Public Health. Block randomization based on diabetes (with or without) status. The randomization tables will be mailed to each institution where a member of the research team will oversee the randomization process and group assignment.

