### **Lost to follow up patients**

To prevent patients being lost to follow-up, patient's contact details, including next of kin contacts will be collected initially and updated regularly by the research team. The research coordinators will educate the patient on the importance of contact with the research team throughout the study. Repeated attempts will be made to locate and obtain pertinent medical information for patients who are initially lost to follow-up. A patient will be classified as lost to follow up only if he/she has failed to return for the required study visits and his/her vital status remains unknown despite multiple attempts to contact him/her via telephone, fax, e-mail, certified letter or through patient locator agencies (if allowed by national regulation). The informed consent forms will include language to grant the option to employ outside companies to assist in obtaining updated contact information or ascertainment of vital status of lost patients using publicly available source.

**Study Sites:** This study will be performed at 4 academic institutions:

**Grady M. Hospital: Endocrinology section:** [name], CDE (Principal investigator), [name], MPH, [name], [name], [name], MPH  
**-Cardiology section:** [name], MPH, [name]

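### Randomisation is blocked by diabetes, but the primary test ignores it and the adjusted model need not keep it: a small effect with a free fix

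*Combined protocol and SAP*

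**What the plan says.** Under *Randomization and Blinding* the plan specifies "Block randomization based on diabetes (with or without) status". No other blocking factor is named. The same section says "The randomization tables will be mailed to each institution", and the *Study Sites* paragraph adds "This study will be performed at 4 academic institutions".

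*Sample Size and Power Calculations* sizes the trial "Based on two-sided Chi-square test, with preserved alpha=0.05" and states that "we would achieve over 80% power to detect a 30% reduction in proportion of patients" at a 50% placebo rate.

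*Analysis of Primary Endpoint* begins by comparing the proportion with at least one event "between the two study groups, using Chi-squares test or Fisher"'s exact test, with no stratum. Then "Logistic regression will be conducted to adjust for the effects of other potential confounders (e.g. age, gender"), and "Stepwise, backward, or forward model selection strategy will be adopted to determine the variables to be included in the final model". The plan fixes no selection algorithm, threshold, candidate list or forced term.

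*Stopping Due to Overwhelming Evidence of Efficacy* plans a group sequential test at 70% of patients and does not name the statistic.

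**The concern.** Three things are left loose.

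- **The analysis does not follow the randomisation.** Blocking on a prognostic factor makes the arms more alike than a crude test assumes, so the crude test is somewhat conservative and gives up a little power.
- **The adjusted odds ratio may omit the blocking factor.** Whether diabetes is in the model would depend on its p-value in these data.
- **The deciding p-value is implied, not stated.** Two crude tests and three selection algorithms are allowed. If more than one result could be claimed, the 5% level is no longer protected. If Fisher's test were chosen, the power promised for the chi-square would not be delivered.

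**Working it through.** **1. The plan's own figure.** With n = 176 per arm, p0 = 0.50, p1 = 0.35 and mean 0.425:

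- SE under the null = √(2 × 0.425 × 0.575 / 176) = 0.0527
- SE under the alternative = √((0.50 × 0.50 + 0.35 × 0.65) / 176) = 0.0521
- Power = Φ((0.15 - 1.96 × 0.0527) / 0.0521) = Φ(0.897) = 81.5%

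The plan says 82%, so this reproduces. So does 176 / 0.9 = 195.6, rounded up to 196 per arm. The same formula gives 66.3% and 74.3% at placebo rates of 40% and 45%, where the plan's table has 62% and 72%. That discrepancy is separate from this point.

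**2. Chi-square against Fisher.** Exact binomial enumeration, 176 per arm, 30% relative reduction:

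| Placebo rate | Chi-square | Fisher |
|---|---|---|
| 40% | 66.4% | 62.2% |
| 45% | 74.8% | 71.1% |
| 50% | 81.1% | 77.9% |
| 55% | 87.3% | 84.9% |
| 60% | 92.3% | 90.6% |

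Fisher's actual type I error is 3.7 to 3.8%. The smallest expected cell over this range is 176 × (0.40 + 0.28) / 2 = 59.8, so small cells give no reason to use it.

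**3. How prognostic diabetes might be.** The plan does not give the event-rate gap between strata. It cites a registry with 45.3% diabetes and a readmission hazard ratio of 1.46. Taking p(diabetes) = 1 - (1 - p)^1.46, with p the rate without diabetes and an overall rate of 50%, gives 44.1% without and 57.2% with diabetes. The check is 0.547 × 0.441 + 0.453 × 0.572 = 0.500. The risk ratio is 57.2 / 44.1 = 1.30. Diabetes then explains 0.453 × 0.547 × 0.131² / 0.25 = 1.7% of the placebo-arm outcome variance, which is why the gain from stratifying is small.

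**4. Crude test against CMH.** Simulation of 40,000 trials per setting: N = 352, 45.3% diabetes, blocks of 4 within diabetes, the same diabetes risk ratio in both arms, no continuity correction, null rate 42.5%:

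| Diabetes risk ratio (assumed) | Power, chi-square | Power, CMH | Type I, chi-square | Type I, CMH |
|---|---|---|---|---|
| 1.0 | 81.19% | 81.10% | 4.81% | 4.76% |
| 1.2 | 81.20% | 81.32% | 4.81% | 4.88% |
| 1.30 | 81.76% | 82.18% | 4.70% | 4.85% |
| 1.46 | 80.91% | 81.99% | 4.58% | 5.06% |

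The differences are -0.1, +0.1, +0.4 and +1.1 points. Power levels vary by about half a point between runs (a second run at 1.30 gave 81.6% for CMH), but both tests are applied to the same simulated trials. In that second run the continuity correction lowered CMH power to 78.5%.

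**5. The selected model.** The assumptions are a risk ratio of 1.30, 12 candidates (diabetes, 4 prognostic, 7 noise) with pairwise correlation 0.2, entry at p<0.05, and treatment always kept. The joint SD of the covariates on the logit scale is varied. Power uses 8,000 trials and the null 16,000 (95% half-width 0.35 points):

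| Covariate SD | 0 | 0.4 | 0.7 | 1.0 |
|---|---|---|---|---|
| Power, forward selection | 81.9% | 83.2% | 85.3% | 88.0% |
| Power, fixed six-term model | 81.8% | 83.6% | 85.4% | 88.1% |
| Type I, forward selection alone | 5.3% | 5.2% | 5.2% | 5.2% |
| Type I, crude or any selected model | 5.5% | 5.9% | 6.4% | 6.8% |
| Type I, CMH or fixed model | 5.7% | 5.9% | 6.3% | 6.6% |

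Forward selection leaves diabetes out in 35 to 43% of trials at p<0.05, 24 to 32% at p<0.10 and 18 to 24% at p<0.157. If only two of the fixed model's four added covariates are prognostic, it still has 82.0, 83.1, 84.3 and 86.3% power.

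A separate simulation with other assumptions (diabetes log odds ratio 0.57, ten further candidates) agrees. Type I error was 6.0% when the crude, backward or forward result could be claimed, and backward selection dropped diabetes in about 27% of trials.

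**The case against.** The strongest reply is that little is at stake. At the risk ratio implied by the plan's own cited hazard ratio, stratifying gains 0.4 points; the 1.1-point figure needs 1.46 to be a risk ratio, which the plan does not say. The crude test errs on the safe side. Selection by itself does no visible harm: it matches the fixed model for power and is close to 5% under the null. Sizing on a chi-square and listing the crude comparison first both suggest that it decides the trial. Fisher reads naturally as a small-cell fallback that would not be used. The named covariates are only examples, so diabetes may well be a candidate.

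Most of this stands, and it limits the point to a small one. It does not remove it. The plan neither names the deciding test nor guarantees that diabetes stays in the model, and there is no offsetting benefit in leaving either open. The either-or inflation is also not specific to selection: CMH plus a fixed model gives nearly the same figures if either may be claimed. Naming one test is therefore what protects the level.

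Two further remarks are fair. The choice of supportive covariates is partly judgement. A CMH test also needs an accompanying effect estimate and a rule for missing baseline laboratory values in the model.

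**Conclusion.** The concern holds, as an improvement that should be made and not as a threat to the trial. Ignoring the blocking factor costs between nothing and about one point of power, and does not inflate type I error. Using Fisher's test would cost about three points and take power below 80% in the base case; that result needs only the plan's own rates. The 5.5 to 6.8% type I error arises only if either p-value may be claimed, and it rests on assumed covariate strength, correlation and candidate numbers. The rates at which diabetes is dropped rest on the same assumptions and on an entry threshold the plan does not give. The text itself is not in doubt: blocking is by diabetes, the first test is unstratified, and no term is forced into the model.

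**What to change.** 1. **Name one confirmatory test.** State that the 26-week proportion is tested by a two-sided CMH test stratified by diabetes, without continuity correction, at the 70% look and at the final analysis. Delete the Fisher option for the primary endpoint. State the effect estimate and interval that go with it, and base the conditional power at the 50% interim on the same statistic.
2. **Replace the selection sentence with one supportive logistic model:** treatment, diabetes, age, gender, log NT-proBNP and eGFR, all kept regardless of p-value. Fix the list, and the handling of missing baseline values, before the 50% interim unblinds the DSMB. LVEF is left out because the echocardiogram window is 12 months in *Inclusion Criteria* and 6 months in the *Schedule of Assessments* footnote.
3. **Confirm whether the tables sent to the institutions are also blocked by site.** Only diabetes is named, so site is left out here. If site was a blocking factor, an eight-stratum CMH costs 0.2 to 0.7 power points relative to stratifying by diabetes alone when site has no effect (four sites at assumed shares of 40/30/20/10%).

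**Cost.** SAP wording only. Sample size, endpoint and data collection do not change. Expected events are 176 × (0.50 + 0.35) = 150, or 25 per model term. If diabetes is not prognostic, CMH loses about 0.1 power point.

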### **Study Endpoints:**

**Primary outcome** is to compare the efficacy of dapagliflozin compared with placebo, on the composite rate of hospital admissions, emergency department visits, urgent clinic visits for HF and death after admission with ADHF.

**Secondary outcomes** are to determine differences between dapagliflozin compared to placebo in:

1. Change in the KCCQ score between baseline score and the scores at 12, and 26 weeks
2. Change in the CHQ-SAS score between baseline score and the scores at 12, and 26 weeks
3. Change in NT proBNP levels between baseline and after 12 and 26 weeks
4. Change in 6-minute walk distance (6MWD) between baseline and after 12 and 26 weeks
5. Change in HbA1c between baseline and after 12 and 26 weeks (in T2D patients). [SEP]
6. Change in weight between baseline and after 12 and 26 weeks [SEP]
7. Change in systolic blood pressure between baseline and after 12 and 26 weeks
8. Change from baseline in left atrial volume index and other measures of left ventricular systolic and diastolic function in patients who may undergo repeated echocardiogram during follow up.

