### Patients:

Patients admitted with ADHF will be enrolled after signing an informed consent. Patients will be invited to participate during their hospital admission. Those fulfilling the inclusion/exclusion criteria will undergo baseline testing at randomization prior to discharge.

We will recruit 392 patients, hospitalized with ADHF. Patients with T2D can be treated with diet or oral antidiabetic drugs (OAD) except TZDs, or SGLT2-i, or on low-dose insulin therapy (total daily dose [TDD]  $\leq$ 0.4 unit/kg/day) prior to admission.

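### Continuous secondary endpoints: no principal analysis is named, and adjustment for the baseline value, which the trial already collects, is not secured

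*Combined protocol and SAP*

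**What the plan says.** The Study Endpoints section defines the continuous secondary outcomes as changes, for example "Change in the KCCQ score between baseline score and the scores at 12, and 26 weeks". The Patients section places the baseline measurement before treatment: "Those fulfilling the inclusion/exclusion criteria will undergo baseline testing at randomization prior to discharge".

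The Analysis of Secondary Endpoints paragraph under Statistical Methods then sets out three steps for these outcomes:

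1. "we will first conduct cross-sectional analyses based on nonparametric Wilcoxon tests (or t-tests";
2. "followed by multivariate linear regression, where responses may be transformed to better meet the normality assumption";
3. "Then we will apply repeated measures ANOVA or repeated measures linear regression model to assess the outcome differences between the two study groups".

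No covariate is named for step 2 or step 3. The paragraph ends: "Standard model selection and checking procedures will be applied to ensure the adequacy of the adopted models". It does not say which step is the principal analysis of any endpoint. By contrast, the Cost-Effectiveness Analyses paragraph does commit to a baseline covariate for repeatedly measured cost outcomes: age, gender, race, insurance and duration of diabetes, "along with baseline utility score, will be adjusted".

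The same secondary-endpoint paragraph lists week 6 among the KCCQ time points. The Study Endpoints section and the Schedule of Assessments have no week-6 KCCQ.

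**The concern.** Three analyses of each endpoint are planned and none has priority, so the reported result could be chosen after the data are seen. Only a model that contains the baseline value uses the information the trial has already paid for in its baseline visit. Step 1 cannot contain it. Steps 2 and 3 may or may not, and a data-driven selection could keep it for one endpoint or visit and drop it for another.

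Step 3 does not settle the matter by itself. Allowing for the correlation between the week-12 and week-26 values is not the same as adjusting for baseline. If the changes are modelled without a baseline term, or if baseline is simply one more level of a repeated-measures ANOVA with complete data, the treatment contrast is still the raw difference in mean change.

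At stake is the precision of the Aim 2 results (symptoms, quality of life, NT-proBNP, HbA1c) and how far a chance difference between the arms at baseline shows up in the observed contrast.

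**Working it through.** **The plan's own figure.** No secondary endpoint has a stated power, so the only sample-size figure to carry over is the primary one ("Based on two-sided Chi-square test, with preserved alpha=0.05"). With 50% against 35% and 176 per group:

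Φ[(0.15 − 1.96·√(2·0.425·0.575/176)) / √((0.50·0.50 + 0.35·0.65)/176)] = Φ(0.897) = 81.5%, against 82% stated. For attrition, 176/0.90 = 195.6, hence 196 per group and 392 in total. Both reproduce, with 176 read as per group.

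**Precision of the two analyses.** Let s0 and s1 be the standard deviations at baseline and follow-up, and r their correlation. Per patient:

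- unadjusted change score: s1² + s0² − 2·r·s0·s1
- baseline-adjusted: s1²·(1 − r²)
- difference: (s0 − r·s1)², which is never negative.

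So in large samples adjustment does not lose precision, whatever r is; it costs one degree of freedom. With s0 = s1 = s the two variances are 2(1 − r)s² and (1 − r²)s², and their ratio is (1 + r)/2.

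| r (assumed) | variance ratio | interval narrower by 1 − √ratio |
|---|---|---|
| 0.3 | 0.65 | 19.4% |
| 0.5 | 0.75 | 13.4% |
| 0.7 | 0.85 | 7.8% |
| 0.9 | 0.95 | 2.5% |

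A simulation of 4,000 normal-data trials per value gave ratios of 0.67, 0.74 and 0.84 at r = 0.3, 0.5 and 0.7.

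**Illustration on KCCQ.** Inputs: a 5-point difference (the Measurements During follow-up section calls a change of this size small but meaningful); 176 per group (borrowed from the primary endpoint); two-sided 0.05; r = 0.5 and SD 20 or 25 (both assumed).

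- SD 20, change score: SD of change 20·√(2·0.5) = 20; SE 20·√(2/176) = 2.132; Φ(5/2.132 − 1.96) = Φ(0.385) = 65%.
- SD 20, adjusted: 20·√0.75 = 17.32; SE 1.846; Φ(0.748) = 77%.
- SD 25, change score: SE 2.665; Φ(−0.084) = 47%.
- SD 25, adjusted: SD 21.65; SE 2.308; Φ(0.206) = 58%.

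In the simulation at SD 20 and r = 0.5, the t-test, Wilcoxon test and baseline-adjusted analysis had power of 65%, 63% and 77%.

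**Where one model will not fit every endpoint.**

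- HbA1c is analysed in T2D patients only, so a diabetes term would be constant.
- Follow-up echocardiography is scheduled at week 12 only, and the Study Endpoints section restricts it to patients who may have a repeat examination.
- In the Schedule of Assessments as extracted, the first 6-minute walk is at week 2, after treatment starts. The table may have been broken in extraction, so this needs checking.

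**The case against.** The strongest reply is that the unadjusted tests are only the opening step. Regression and repeated-measures models follow in the same paragraph, they could well include baseline, and the cost paragraph shows that the authors know how to use a baseline covariate. This stands. A reader might infer that the Aim 2 endpoints will be judged on raw change scores and that their intervals will therefore be too wide. The documents do not say so: they leave the principal step and the covariates open. The loss is conditional on the unadjusted step being the one reported, or on baseline being left out of the later models.

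A reader might also infer that the unadjusted comparison is biased, or that regression to the mean is especially strong because baseline is taken at the end of an admission for decompensated heart failure. Neither is supported. Under randomisation the change-score comparison is unbiased on average, and chance imbalance matters for precision and for the estimate conditional on the imbalance that occurred. The documents give no figure on regression to the mean after such an admission.

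The power figures have limits too. They compare single-visit analyses, not the plan's final repeated-measures step with the proposed model. The 176 per group cannot apply to HbA1c, and patients who die have no week-26 score. The 5 points is a meaningful change in score, not a planned difference between arms. The gain is small if r is near 1.

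What remains is that the plan does not secure the adjustment, and that securing it is free. Permission to transform responses likewise does not fix the scale for NT-proBNP in advance.

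**Conclusion.** The point holds as a free improvement to the secondary analyses. The plan neither names a principal analysis for the continuous secondary endpoints nor commits to the baseline value, or to diabetes status, by which randomisation is blocked, as a covariate.

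Against an unadjusted change score, the gain is an interval narrower by between 19% (r=0.3) and 2.5% (r=0.9). The direction follows from the algebra. The size rests on an assumed r and on equal variances at baseline and follow-up. The rise in KCCQ power at r=0.5 (65% to 77% at SD 20, 47% to 58% at SD 25) is illustrative only, since the documents give neither r nor SD. The text does not establish that these losses will occur, only that nothing prevents them. The primary endpoint and the sample size of 392 are not affected.

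**What to change.** Rewrite the Analysis of Secondary Endpoints paragraph to name one principal analysis per continuous endpoint:

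- **KCCQ, CHQ-SAS, NT-proBNP (log scale, including its baseline), weight, systolic blood pressure, magnesium:** one repeated-measures model of the week-12 and week-26 values, with arm, visit, arm-by-visit, baseline value, baseline-by-visit and diabetes stratum as fixed terms exempt from selection. With these baseline terms, modelling the value or the change gives the same treatment effect, so the endpoint definitions can stay.
- **HbA1c:** the same model in T2D patients, without the diabetes term.
- **Echocardiographic measures:** baseline-adjusted ANCOVA at week 12.
- **6-minute walk distance:** first confirm that a pre-treatment test exists. If it does, use the repeated-measures model.

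Keep the Wilcoxon or t-tests as supportive analyses. Separately, delete week 6 from the KCCQ time points in that paragraph, since neither the endpoint list nor the schedule collects it.

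The cost is a change to the analysis text, with no new patients. No new data are needed either, subject to the check on the 6-minute walk baseline. It should be made before any unblinded comparison of the secondary endpoints.
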